**Statistical Analysis:** *Power analysis and sample size calculation:* The sample size calculation was based on power estimates using our preliminary data on how acute postoperative pain contributes to PPP using the SAS "powerlog" macro. An updated analysis of our multi-center (three) chronic pain after total knee and hip arthroplasty survey study, evaluated one yr postoperatively, provided data for sample size calculation. The one yr follow-up data from this survey provides a conservatively estimate for the incidence of PPP at 6 mo, our primary outcome. To evaluate the effect of acute postoperative pain on incidence of PPP, our multi-center data was stratified based on chronic pain using our PPP criteria. Across the three centers, 259 TKR patients fell within criteria, of which 46 (17.8%) were identified with PPP at one year after surgery. Using a logistic regression, the acute postoperative NRS pain intensity was significant ( $P=0.0005$ ) with an odds ratio of 1.24 for each 1 point increase in acute postoperative NRS pain (95% Wald Confidence limits: 1.098-1.390). The average acute postoperative NRS pain for the entire sample was 5.5 (SD=2.9). Using the data to estimate predicted probability of PPP at the mean acute postoperative pain level, we have an incidence of 15.5% at the mean and 30.3% at the mean plus one standard deviation (NRS=8.4). A power analysis with 90% power and alpha of 0.05, using a logistic regression with no other covariates gives us a required sample size of 130. However, because we plan on utilizing multiple covariates, we estimate the multiple squared correlations at 0.5, raising our sample size estimated to 259. With a 15% dropout rate this values climbs to 298 (round to 300).

**Blinding of data:** To reduce bias, each co-investigator will only be involved in measurements specifically related to their specialization (Pain, Neurophysiologic, Psychosocial or Functional outcomes) and no others.

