**General statistical analysis:** Descriptive statistics will be reported as mean and standard deviation (SD) for continuous normally-distributed variables, and reported as counts and percentages for dichotomous variables. Assumptions will be evaluated and, if violated, either corrective measures will be taken (data-transformation) or other less restrictive methods will be implemented. Error inflation for multiple pre-planned comparisons will be corrected by using the Bonferroni step-down method. Models will be examined with no risk factors, with individual risk factors, and with multiple risk factors. The distribution of the primary outcome, NRS pain scores at 6 mo, will be evaluated, transformed to normal and then modeled as a continuous variable. If this is not possible, *then the dichotomous version*, as defined for PPP, will be used. We expect that the primary outcome of PPP (dichotomous) will be modeled using a logistic regression because the distribution of NRS pain scores from our preliminary survey data was strongly bi-modal (modes:0, 3). Thus it appears that this kind of distribution represents two distinct populations (a normally distributed pain population and a unimodal 'no-pain' population). Pain intensity (continuous) will be separately modeled for those patients who report a non-zero pain level. Risk factors will be evaluated, for **independent** association with the outcome variable, first for linearity and then for model fit using backward stepwise logistic regression (criterion  $P<0.05$ ). Model fit will be assessed by the Hosmer-Lemeshow test and validity of the fit models and predictive accuracy will be assessed using bootstrapping methods as well as the AUC 'c-index'. Analysis will also be performed on the raw NRS score (at 6 mo) using general linear models and mixed model regression as this may elucidate additional details about relationships among the factors and how they relate to pain at 6 mo. **Mediation** models will be evaluated based on techniques pioneered by Baron and Kenny, but with the modification of bootstrapping techniques to produce multiple mediator results with confidence intervals. Sobel method and  $R^2$  effect-size measures will be used to test and evaluate the mediation effects as well. Distributional assumptions and

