model fit will be evaluated for all models. **Moderating** effects will be tested using model building with predefined interactions for linear or logistic models.

Due to the extensive monitoring designed into our protocol we do not expect a large amount of missing data; however, the missing data that does arise will be handled using multivariate multiple imputation. Data not assumed to be missing at random, will be evaluated for systematic effects using sub-groups stratification. Statistical analyses will be performed using SAS version 9.1 (SAS Institute Inc, Cary, NC) or SPSS (SPSS for Windows, Rel. 16.0.1. 2007. Chicago: SPSS Inc.), with statistical significance determined with a Type I error threshold of  $\alpha = 0.05$ . For continuous outcome mediation analysis we will use a SAS macro (INDIRECT macro) and for dichotomous outcomes the SPSS macro version (INDIRECT macro) will be used, as the SAS macro version does not allow for dichotomous outcome variables.

**Primary endpoint:** The *primary endpoint* for the **Primary Aim** will be the incidence of PPP after TKR (similar to our power analysis), evaluated at 6 mo. For the **Secondary Aims**, the *primary endpoint* will be functional outcomes (ROM, WOMAC, SF-36,).

**Secondary endpoints:** The *secondary endpoint* for the Primary and Secondary Aims will examine additional parameterizations of PPP at 6 mo (NRS pain non-dichotomous, StEP neuropathic pain examination). Use of raw NRS pain scores may highlight functional (e.g. linear) relationships between pain and the predictive factors. Analysis will be performed as described for the primary outcome variable (incidence of PPP) but with the re-parameterized outcome variable and different model assumptions, depending on distributional properties. Each re-parameterization will be evaluated with respect to and compared with the primary outcome.

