### **Detailed Analyses:**

**Primary Aims:** are to investigate the relationships of *risk factors* and the development of PPP at 6 mo post-TKR, through independently predictive (for clinical prediction models, Hypothesis 1) and mediated models (to reveal underlying mechanisms, Hypothesis 2). These risk factors are preop thermal pain sensitivity; anxiety and catastrophizing; postop area of secondary mechanical hyperalgesia and pain intensity.

A. **Independent Risk Factors:** Risk factors will be individually predictive of the PPP (primary endpoint):

*Hypothesis 1 is that greater (↑) preop pain sensitivity, higher levels of preop pain anxiety and catastrophizing, larger areas of secondary hyperalgesia post-TKR and higher postop pain intensity will independently predict increased incidence of PPP at 6 months post-TKR.*

- 1) **Pain Intensity:** Expected Result: (Hypothesis 1): Higher postop pain intensity (↑), will independently predict increased incidence of PPP at 6 mo post-TKR (ex. ↑ postop NRS → ↑ PPP incidence).
- 2) **Neurophysiologic:** Expected Result: (Hypothesis 1): Greater preop pain sensitivity (↑) and larger areas of secondary hyperalgesia ( $\text{cm}^2$ ) post-TKR will independently predict increased incidence of PPP at 6 mo post-TKR (ex. ↑ preop thermal pain sensitivity → ↑ PPP incidence).
- 3) **Psychosocial:** Expected result: (Hypothesis 1): is that greater (↑) catastrophizing (PCS score) will independently predict increased incidence of PPP at 6 months post-TKR (ex. ↑ PCS score → ↑ PPP).
- 4) **Demographics:** Expected result: Patients 65-85 yrs will have a lower incidence of PPP than patients 18-64 yrs.

B. **Mediation Models:** Effects of preoperative factors on development of PPP occur through interrelated neurophysiologic mechanisms:

*Hypothesis 2 is that the effects of preoperative factors on development of PPP occur through interrelated neurophysiologic mechanisms. Thus, it is expected that the area of secondary hyperalgesia post-TKR will mediate links between preoperative pain sensitivity and PPP incidence, as well as mediate links between pain anxiety/catastrophizing and PPP incidence at 6 mo after TKR.*

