- 1) **Neurophysiologic:** Expected Result: (Hypothesis 2): Area of secondary hyperalgesia post-TKR will mediate links between preoperative pain sensitivity and PPP incidence: (preop thermal sensitivity score affects area of mechanical secondary hyperalgesia which in turn leads to increased PPP incidence) will fit the data significantly better than the independently predictive model (preop thermal sensitivity score will directly affect PPP incidence).
- 2) **Psychosocial:** Expected result: (Hypothesis 2): Area of secondary hyperalgesia will mediate links between pain anxiety/catastrophizing and PPP (ex. pain anxiety PASS score → area of secondary hyperalgesia → PPP incidence).

**Secondary Aims:** Test for risk moderators.

C. **Moderation Models:** Test for risk moderators:

*Hypotheses 4 postulates that patient age will moderate the relationship between risk factors and PPP development. We expect the predictive relationship between preop pain sensitivity and PPP incidence to be stronger (enhanced) among younger as opposed to older patients*

- 1) **Demographics:** Expected Result: The effect of preop pain sensitivity on PPP will be moderated by age (ex. direct effect is: ↑ preop thermal NRS score → ↑PPP incidence; but moderating effect is: ↑ preop thermal NRS score x ↓age → ↑↑PPP incidence)

**Omnibus Model:** To create a more complete description of the factors, mechanisms and interrelationships involved in development of PPP, several omnibus models will be created and evaluated. Knowledge gained from each of the individual aims will be utilized to create this model, using principal component and factor analysis for variable reduction and predictive modeling with particular focus on mediation between the domains and the aims.

**The prediction equation:** To highlight the risk factors for PPP, including importance (weighting) and interactions, in not only the preoperative phase but in the postsurgical phase, a prediction equation will be described. The use of the prediction equation can then be validated and fine tuned in later studies. A simple example formula for the prediction equation:

$$Pr_i = \frac{1}{1 + \exp(a + \beta_1 Age_i + \beta_2 preOpPainSens_i + \beta_3 SecHyperal_i + \beta_4 postOpNRS_i + \beta_5 TraitAnxiety_i + \beta_6 Catastrophizing_i)}$$

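### The better-fit criterion stated for the neurophysiologic half of Hypothesis 2 does not test mediation, and nothing says whether it or the planned indirect-effect methods decide.

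*Combined protocol and SAP*

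**What the plan says.** Under Primary Aims in the Detailed Analyses, Hypothesis 2 is the mechanistic arm: "it is expected that the area of secondary hyperalgesia post-TKR will mediate links between preoperative pain sensitivity and PPP incidence", with a parallel statement for pain anxiety and catastrophizing. Item B.1 (Neurophysiologic) then gives an expected result. The model running from thermal sensitivity through hyperalgesia area to PPP "will fit the data significantly better than the independently predictive model", the latter being the model in which sensitivity acts on PPP directly. No fit statistic is named, and the two models are not said to be nested. Item B.2 (Psychosocial) carries no fit criterion.

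The methods are in the General statistical analysis section. Mediation "models will be evaluated based on techniques pioneered by Baron and Kenny", with bootstrapping added "to produce multiple mediator results with confidence intervals". The Sobel method and R² effect-size measures "will be used to test and evaluate the mediation effects as well". Software is named: "for dichotomous outcomes the SPSS macro version (INDIRECT macro") is to be used. The general threshold is α = 0.05, without a stated sidedness. No sentence ranks these methods against each other or against the fit comparison.

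**The concern.** An indirect effect needs two links: preoperative sensitivity to area, and area to PPP. A comparison of PPP models with and without area looks only at the second. Hypothesis 1 already expects larger areas to predict PPP. If that expectation is right, the fit criterion will tend to be met whether or not sensitivity has any effect on area.

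The stake is the mechanistic conclusion of a primary aim. Where the fit comparison is positive and the interval for the indirect effect includes zero, the plan does not say which result stands, and a report could say that the stated expected result was met. The Multi-Factorial Approach section intends such findings to point to targets for intervention, including drug treatment aimed at secondary hyperalgesia, so a falsely claimed mechanism would have consequences.

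**Working it through.** **Plan's own figure.** There is none to reproduce. The power analysis ("A power analysis with 90% power and alpha of 0.05") concerns acute pain as a predictor of PPP. No power or error rate is given for any mediation test.

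**Inputs from the Power analysis section.** PPP incidence 17.8%. Evaluable patients: 300 × (1 − 0.15) = 255. Alpha 0.05, taken as two-sided.

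**Assumptions.** X (sensitivity) and M (area) are standardised and normal, with no other covariates. The area odds ratio (OR) per SD ranges from 1.0 to 1.87. The top value is borrowed from the acute-pain effect, 1.24 per point over an SD of 2.9: 1.24^2.9 = 1.87. It belongs to a different predictor. The direct OR of X is 1.5; results without a direct effect are similar.

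**Nested reading: PPP on X + M against PPP on X.** The likelihood-ratio test has one degree of freedom and tests the M coefficient alone. Take X and M as independent, so that no mediation exists. The chance of a significant result is then the power of the area-to-PPP test, approximately

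1 − Φ(1.96 − ln(OR) × √(n·p·(1 − p))), with √(255 × 0.178 × 0.822) = 6.11.

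- OR 1.24: ln = 0.215, product 1.31, power 26%
- OR 1.3: ln = 0.262, product 1.60, power 36%
- OR 1.5: ln = 0.405, product 2.48, power 70%
- OR 1.87: ln = 0.626, product 3.82, power 97%

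At OR 1.0 the rate is the test's own 5%.

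If both paths must be significant, the rate with no X-to-M link is about 0.05 times that power. At OR 1.87 this is 0.05 × 0.97 = 4.8%.

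Simulation agrees with both approximations (share of studies declaring mediation when none exists):

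| Area OR per SD | Nested fit test | Both paths significant | Sobel |
|---|---|---|---|
| 1.0 | about 5% | 0.4% | 0% |
| 1.24 | about 25% | 1.2% | 0% |
| 1.3 | about 35% | about 2% | under 1% |
| 1.5 | about 70% | 2.9% | 0.5% |
| 1.87 | about 95% | 4.3% | 1.4% |

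Percentile bootstrap intervals for the indirect effect excluded zero in 0% (OR 1.0), 0.3% (OR 1.24) and about 6% (OR 1.87; Monte Carlo standard error about 1.7 points).

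**Does the fit test respond to mediation at all?** Hold the area OR at 1.87 and set the X-to-M path to 0, 0.2 and 0.3. The nested fit test is positive in 96%, 94% and 94% of studies, so it does not distinguish the three cases. Requiring both paths gives 4%, 84% and 93%.

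**Non-nested reading: X to M to PPP with no direct path, against X to PPP.** The PPP parts of the two models use different predictors, so neither contains the other and the ordinary likelihood-ratio test does not apply. Ranking by likelihood does not help either. With no mediation and area ORs of 1.5 to 1.87, the area-only model has the higher likelihood in about 92–99% of studies without a direct effect, and in roughly half to four-fifths with a direct OR of 1.5. That is a ranking and not a significance test.

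**The case against.** The strongest reply is that the sentence is an expected result and not an analysis rule. It is written in the same style as the other expected results, and its grammar is broken. The methods section already prescribes Baron and Kenny steps, which include the sensitivity-to-area path, together with bootstrap intervals, Sobel tests and an indirect-effect macro. The sentence itself also describes a model with both links. It covers only one of the two mediation models. Finally, the documents give no area effect, so the error rates depend on assumed odds ratios; at 1.24 the rate is about 25%, and at 1.0 it is 5%.

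Most of this stands, and it limits the point. A reader might infer that the plan will often claim mediation where there is none. The documents do not support that. It would follow only if the nested fit comparison were allowed to decide, and no section says so. Under the indirect-effect methods already planned, false claims stay at about 6% or less in the same scenarios. Nor does the problem cover all of Hypothesis 2, since the psychosocial half carries no fit wording.

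The objection does not remove the inconsistency. The fit comparison is the only result the Detailed Analyses state as evidence for that hypothesis, it does not measure an indirect effect on either reading, and nothing places it below the other methods. Naming both links in the model does not rescue it, because comparing how well PPP is fitted does not test the first link.

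**Conclusion.** The point holds as an inconsistency in the decision rule for a primary-aim hypothesis. The stated fit criterion for the neurophysiologic model can be met without mediation, and the plan leaves open whether it or the indirect-effect methods settle the claim.

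Its size is conditional on the nested reading and on the fit comparison deciding: about 25% to 95% of studies would meet the criterion with no sensitivity-to-area link at area odds ratios per SD of 1.24 to 1.87, against about 6% or less when both paths are required. These figures rest on 255 evaluable patients, 17.8% incidence, standardised normal predictors, no covariates and assumed area effects. The reasoning does not depend on them, because a test of the area-to-PPP link alone cannot establish an indirect effect. The change is worth making before analysis.

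**What to change.** 1. In Detailed Analyses, B.1, remove the statement about better fit, or label the comparison descriptive.
2. In General statistical analysis, add one decision rule: each mediation claim under Hypothesis 2, neurophysiologic or psychosocial, is supported only if the bootstrap 95% confidence interval for the indirect effect (preoperative factor to area, times area to PPP) excludes zero. Sobel tests and R² measures are reported as supportive.

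The cost is about two sentences. The bootstrap analysis is already planned, and no new data, visits or patients are needed.

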#### Potential Difficulties and Limitations

1. We have no way of directly assessing minor nerve damage following TKR.
2. Patient may decide to undergo another elective joint replacement procedure during the 6-mo postop period
3. Although power analysis is based on 17.8% PPP incidence, TKR procedures may vary over the 3-yr duration of study. However our power estimates are conservative and our multivariate analyses are robust and powerful.
4. 6 mo assessment of PPP can be complicated by opioid use in some patients. However, this factor is considered as a covariate in the analysis.

#### Future Directions

- Modeling of disease trajectory: Change over time (presurgery to 6 mo) for risk factors (e.g. secondary hyperalgesia) and dynamic interactions will be modeled using analytic techniques such as growth curve models to model the dynamic etiology of PPP. Trajectory information is critical to describe and identify critical time points for intervention.
- The blood sample analysis of DNA and RNA expression for “pain genes” (from blood collected on the day of surgery) can be completed and lead to future incorporation of genetic risk factors for prediction of PPP incidence.
- Results from this study will enable researchers to construct enriched enrollment clinical trials with patients at high risk for developing PPP. This will enable therapeutic interventions that can lead prevention of PPP.

